8.4.3 Electrocardiograms

Not applicable as electrocardiograms were not collected in this study.

8.4.4 Other safety variable(s)

The number and percent of autoantibody levels (ANA and anti-dsDNA antibody) will be presented as normal or antibodies present for ANA, and as negative or positive for anti-dsDNA antibodies. This table will be presented for the CZP Low Dose group, CZP High Dose group, and for the All CZP Doses group. A similar table will be presented by age group.

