9.6.10 Autoantibodies

Autoantibody (ANA and anti-dsDNA) titers will be determined every 12 weeks starting at Week 14, and at the Completion/ET and SFU Visits.

Instructions on blood sample collection, processing, storage, and shipping will be provided in the laboratory manual for this study.

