13.3 Planned safety analyses

All safety summaries will be based on the Safety Population as a whole, by treatment group, weight, and age stratum.

Treatment emergent adverse events will be summarized descriptively by primary SOC, high level term, and PT. Additional tables will summarize AEs by severity and relationship to study drug, and separate tables will be generated for AEs leading to withdrawal from the study, SAEs, and deaths. Other AEs of special interest including, but not limited to, infections will also be summarized.

The specific set of AEs reported as injection reactions will also be summarized along with their classification as either injection site reactions or systemic hypersensitivity reactions (the latter being further classified as acute or delayed).

Actual laboratory values and changes from Baseline in laboratory values will be summarized. Shift tables to show the change from Baseline in the absolute values and details of treatment emergent markedly abnormal values (based on Common Terminology Criteria for Adverse Events criteria) will be presented by variable.

Actual vital signs values and change from Baseline in vital signs values will be summarized.

Autoantibody levels will be assessed via the presence or absence of ANA and anti-dsDNA, and data will be summarized.

Extent of exposure to treatment will be presented descriptively.

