2.2 Study variable(s)

2.2.1 Safety variable(s)

- Adverse Events
- Laboratory parameters (hematology, biochemistry, urinalysis)
- Vital signs
- Autoantibodies (ANA and anti-dsDNA antibody)

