8.3 Clinical laboratory evaluations

Actual laboratory values will be summarized descriptively by week, by dose group and Total. Change from Baseline to last available visit with laboratory values will be summarized descriptively by dose group and Total. If multiple laboratory assessments are taken at the last visit with available data, the last assessment will be used.

Shift tables that cross-tabulate Baseline (low, normal, high relative to normal range, and missing) by end of trial status will be presented by dose group and Total for each laboratory parameter.

The incidence rate of treatment-emergent markedly abnormal laboratory values (based on Common Terminology Criteria for Adverse Events criteria) will be presented by dose group and Total for hematology and biochemistry laboratory parameters only. See Section 13.1 for markedly abnormal criteria.

All laboratory values will be listed with markedly abnormal laboratory values flagged.

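### The planned autoantibody table (SAP 8.4.4) has no Baseline, shift or time point, so it cannot separate pre-existing from treatment-emergent ANA or anti-dsDNA

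*SAP*

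**What the plan says.** SAP 2.2.1 and Protocol 4.1 list four safety variables: adverse events, laboratory parameters, vital signs and autoantibodies. For the last of these, SAP 8.4.4 says that results "will be presented as normal or antibodies present for ANA, and as negative or positive for anti-dsDNA antibodies". It adds: "This table will be presented for the CZP Low Dose group, CZP High Dose group, and for the All CZP Doses group". A similar table is planned by age group, and the section says nothing more.

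Protocol 13.3 is no more specific: "Autoantibody levels will be assessed via the presence or absence of ANA and anti-dsDNA, and data will be summarized".

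On data collection, Protocol 9.6.10 says: "Autoantibody (ANA and anti-dsDNA) titers will be determined every 12 weeks starting at Week 14, and at the Completion/ET and SFU Visits". Table 5-1 fills the Entry column for autoantibodies from C87035.

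For laboratory parameters, by contrast, SAP 8.3 plans "Shift tables that cross-tabulate Baseline" category against status at the end of the trial. SAP 3.3 gives a general Baseline definition, the last non-missing value before the first dose in C87035, but 8.4.4 does not use it.

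**The concern.** A positive ANA or anti-dsDNA result during CR0012 can mean two things. The child may have been positive before ever receiving certolizumab pegol, or may have become positive on it. Only the second bears on drug safety. The protocol gives a reason to care: its Introduction lists drug-induced lupus among the serious events reported with TNF antagonists, and section 9.3 lists lupus and lupus-like illness as an adverse event of interest.

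SAP 8.2 plans no lupus table; the study physician is to identify cases by reading the table of all treatment-emergent events. The autoantibody table is therefore the only planned tabulation aimed at the serological side of this risk. As specified, it mixes pre-existing with new positivity.

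**Working it through.** The plan states no antibody rate, sample size or precision target, so there is no figure to reproduce. The check compares the sections and then illustrates how much the missing Baseline could matter.

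**Step 1. How each named safety variable is summarised.**

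| Variable | Time | Reference to Baseline | Source |
|---|---|---|---|
| Adverse events | during treatment | summarised as treatment-emergent | SAP 8.2 |
| Laboratory parameters | by week | change from Baseline, and Baseline-by-end shift table | SAP 8.3 |
| Vital signs | by week | change from Baseline to last available visit | SAP 8.4.1 |
| Autoantibodies | not stated | none | SAP 8.4.4 |

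Only laboratory parameters get a shift table. The contrast is that each of the other three variables has some reference to the state before treatment and autoantibodies have none.

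**Step 2. What a prevalence figure leaves open.** Inputs: N = 16 subjects (SAP 4.4); k = 4 positive on treatment (assumed for illustration); b = number of those k who were already positive at Baseline (unknown). If no other subject was Baseline-positive and no Baseline is missing, then

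emergent rate = (k − b) / (N − b).

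| b | Table shows | Emergent rate |
|---|---|---|
| 0 | 4/16 = 25.0% | 4/16 = 25.0% |
| 1 | 4/16 = 25.0% | 3/15 = 20.0% |
| 2 | 4/16 = 25.0% | 2/14 = 14.3% |
| 3 | 4/16 = 25.0% | 1/13 = 7.7% |
| 4 | 4/16 = 25.0% | 0/12 = 0% |

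Exact (Clopper-Pearson) 95% intervals at the two ends are 7.3% to 52.4% for 4/16, and 0% to 26.5% for 0/12 (upper limit 1 − 0.025^(1/12) = 26.5%). The planned table prints the same line in all five cases.

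**Step 3. Why a Baseline row alone would not be enough.** Suppose 4 of 16 were positive at Baseline and 4 of 16 at the last visit. If they are the same four children, 0 of 12 Baseline-negatives converted. If they are four different children, 4 of 12 (33.3%) converted and four reverted. The two marginal percentages are identical. Only a within-subject cross-tabulation tells the cases apart.

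**Step 4. Whether a Baseline value is available.** CR0012 collects titers from Week 14. Table 5-1, footnote a, equates CR0012 Week 0 with the last C87035 visit and takes the other entry assessments from the C87035 database. That visit follows treatment in C87035, so it is not a pre-treatment value. Neither document says whether ANA or anti-dsDNA was measured before the first C87035 dose. The Baseline of SAP 3.3 may therefore be missing for some or all subjects.

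**The case against.** Four arguments can be made for leaving the plan alone.

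- **The SAP follows the protocol.** Protocol 13.3 promises only presence or absence. That is correct, and there is no conflict between the documents. The gap is in both.
- **Everything will be listed.** SAP 3.5 provides for listing all available data, and with 16 subjects a reader could trace each child's sequence. This stands in part: the plan as a whole does not hide the information. But a listing is not a defined result, and it shows emergence only if pre-dose C87035 results exist and are merged in.
- **Lupus is reviewed separately.** It is, by the study physician. That covers the clinical event, not seroconversion.
- **The study is small, uncontrolled and descriptive.** No test or decision rule depends on this table. That limits the consequence, but safety is the primary objective and the fix is cheap.

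Two stronger readings are tempting and are not supported. First, from "The number and percent of autoantibody levels (ANA and anti-dsDNA antibody) will be presented as normal or antibodies present for ANA" a reader might infer that repeated samples are pooled, so that a child followed for years counts many times. No passage says so, and SAP 3.1 sets the number and percentage of subjects as the default for categorical parameters. The word for levels is loose, but the unit should be read as the subject. Second, a reader might assume that every sample needed for a Baseline comparison has already been collected. The documents establish the CR0012 sampling only.

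**Conclusion.** The point holds for the table as specified. SAP 8.4.4 names no Baseline, shift or time point, so the table yields prevalence and cannot show treatment-emergent positivity for one of the four named safety variables. In the illustration, a single reported 25.0% covers true emergent rates from 0% to 25.0%. The count of 4 is assumed, as are complete Baseline data and no Baseline-positive subject outside those 4.

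The conclusion is about the table. It does not extend to saying that the study could never separate the two states, since subject listings are planned. Equally, if no pre-dose C87035 results exist, no table can recover them. This is a worthwhile improvement to a descriptive safety summary, and it does not threaten any inference.

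**What to change.** Replace the 8.4.4 table with a subject-level shift table, separately for ANA and anti-dsDNA:

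- Rows: Baseline status under SAP 3.3, as negative, positive or missing.
- Columns: any post-Baseline positive (yes or no), and status at last value. State whether on-treatment C87035 results count as post-Baseline.
- Emergent percentage: Baseline-negative subjects with any post-Baseline positive, divided by Baseline-negative subjects with a post-Baseline result.
- Subjects with no pre-dose C87035 result: shown as Baseline missing and kept out of that denominator.
- Status at CR0012 entry: may be shown separately, labelled as on-treatment entry status. It must not stand in for Baseline. A child who seroconverted during C87035 would then be counted as a pre-existing positive and removed from the denominator, contrary to SAP 3.3.

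The dose-group and age-group presentations can stay.

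The cost is a few sentences in the SAP, one revised table and a merge of C87035 results, with no new sampling in CR0012. The downside is that, if pre-dose results turn out not to exist, only change since CR0012 entry can be reported. The table should then say so in its title or a footnote.

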9 EFFICACY ANALYSES

As the primary objective of this study is to evaluate safety, no primary or secondary efficacy variables are defined. Rather, efficacy variables will be measured to evaluate efficacy of long-term open label treatment with CZP.

All efficacy summaries, where applicable, will be presented by visit, dose group, weight, (20 to <40kg [44 to <88lbs] and ≥ 40 kg [≥ 88 lbs]) and age category (6 to 11 years and 12 to 17 years).

The proportion of subjects in clinical remission and the proportion of subjects in clinical response will be summarized by using the number and percentage of subjects along with associated 95% confidence intervals (CI).

A subject who does not have all required data to derive a response status (response or remission) will be classified as a nonresponder/nonremitter at that particular time point. A subject who withdraws from the study or is reinduced, will be classified as a nonresponder/nonremitter from and including the time of withdrawal or reinduction.

If a subject receives rescue therapy, the subject will be considered as a treatment failure (nonresponder/nonremitter) from the timepoint of administration of first rescue therapy onwards.

Actual PCDAI scores and changes from Baseline in PCDAI scores will be summarized by presenting the mean, standard deviation (SD), 95% CI for the mean, median, minimum, and maximum values.

Levels of CRP and ESR and changes from Baseline in CRP levels and ESR (expressed as a ratio with the value measured at Baseline as denominator) will be summarized by presenting the geometric mean, coefficient of variation, 95% CI for the geometric mean, median, minimum, and maximum values.

IMPACT-III scores and changes from Baseline will be summarized by presenting the mean, SD, 95% CI for the mean, median, minimum, and maximum values.

The change from Baseline in growth score using the Tanner stage (assessing puberty) will be summarized using shift tables. Bone marker values and changes from Baseline in bone marker values will be summarized.

The proportion of days missed from school/work will be summarized by presenting the mean, SD, 95% CI for the mean, median, minimum, and maximum values.

Actual WPAI:CD scores and changes from Baseline in WPAI:CD scores will be summarized by presenting the mean, SD, 95% CI for the mean, median, minimum, and maximum values. Higher scores indicate greater impairment and less productivity. The summaries will be presented separately for the WPAI:CD for children, WPAI:CD for working individuals with CD, and WPAI:CD for caregivers. Each of these 3 questionnaires have 6 questions with the WPAI for working individuals and for caregivers having similar questions, and the WPAI for children having questions which assess time missed and productivity at school rather than at work. In general, the 6 questions are (note that for children, the questions will be similar but related to school):

Questions:

[REDACTED]

The 4 domains are labeled and calculated as (note: domain labels for children will reflect time at school, but domain scores are calculated similarly):

- [REDACTED]: $Q2/(Q2+Q4)$
- [REDACTED]: $Q5/10$
- [REDACTED]: $Q2/(Q2+Q4)+[(1-(Q2/(Q2+Q4))x(Q5/10)]$
- [REDACTED]: $Q6/10$

If appropriate for WPAI, indirect costs parameters will be summarized using descriptive statistics by period of onset.

10 PHARMACOKINETICS AND PHARMACODYNAMICS

10.1 Pharmacokinetics

Plasma concentrations of CZP at each visit will be summarized by anti-CZP antibody status (all subjects, antibody-positive, and antibody negative) for each age category, the overall population, and for each dose group. In addition, plasma concentrations will be summarized by weight category (<40kg; ≥40kg) for the treatment groups.

Individual anti-CZP antibody concentrations will be listed and the incidence of anti-CZP antibody positive subjects will be summarized by study visit and overall incidence by age category and by dose group. Anti-CZP antibody positive status is defined as a subject having a value >2.4 units/mL anti-CZP antibody at any time during the study. If there are more than 1 concentration available for the same timepoint, data will be listed as per the guidance found in the global convention document.

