5.1.1 Study duration per subject

The maximum study duration of CZP treatment may be until the subject reaches the age of 18 years or CZP is approved for use in the US by pediatric subjects with CD. An SFU visit will be conducted 12 weeks following the last dose of study drug.

The end of the study is defined as the date of the last SFU visit of the last subject in the study.

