9.5 Laboratory measurements

Hematology assessments will include the following parameters: red blood cell (RBC) count, hemoglobin, hematocrit, platelets, white blood cell (WBC) count, neutrophils, lymphocytes, monocytes, eosinophils, and basophils.

Clinical chemistry assessments will include the following parameters: Sodium, potassium, total calcium, glucose, creatinine, urea, total protein, albumin, alkaline phosphatase, gamma glutamyl aminotransferase (GGT), aspartate aminotransferase (AST), alanine aminotransferase (ALT), and bilirubin.

For urinalysis, urine protein and blood will be measured by the dipstick method. If positive, microscopic assessments will be done for WBC, RBC, and casts and microbiological culture will be undertaken.

Hematology, clinical chemistry, and urinalysis parameters will be assessed at entry Week 0, every 12 weeks starting at Week 14, and at the Completion/Early Termination (ET) and SFU Visits.

Instructions on blood sample collection, processing, storage, and shipping will be provided in the laboratory manual for this study.

For subjects undergoing reinduction, the parameters ESR, hematocrit, and albumin will be measured at Reinduction Weeks 0, 2, and 4.

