11 PHARMACOKINETICS AND IMMUNOLOGICAL ASSESSMENTS

Blood samples will be collected to determine plasma concentrations of CZP and anti-CZP antibodies every 12 weeks starting at Week 14, and at the Completion/ET and SFU Visits. All of these blood draws will be performed prior to study drug administration (except for the Completion/ET and SFU Visits when there is no dosing) and all of them coincide with the blood collection times for the assessment of hematology and clinical chemistry parameters, so that no additional blood sampling is required at these visits.

Time and date of each blood draw will be documented on the CRF.

Instructions on blood sample collection, processing, storage, and shipping will be provided in the laboratory manual for this study.

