8 SAFETY ANALYSES

All safety summaries will be based on the Safety Population and presented by dose group (separate columns for High Dose and Low Dose), and presented by weight category, and by age category, as appropriate.

For all by-visit AE and medication summaries, if a subject in the Low Dose group is re-induced, the subject will be summarized under the High Dose column from the time of re-induction onwards.

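### Any-time anti-CZP antibody incidence is split by age category, although the age-18 stop makes the number of samples depend on age at entry

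*SAP*

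**What the plan says.** **Duration.** Protocol 5.1.1 allows treatment "until the subject reaches the age of 18 years or CZP is approved for use in the US by pediatric subjects with CD". SAP 2.3.1 repeats this.

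**Sampling.** Protocol 11 schedules blood for CZP concentration and anti-CZP antibodies "every 12 weeks starting at Week 14, and at the Completion/ET and SFU Visits".

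**Analysis.** SAP 10.1 defines a positive subject as one "having a value >2.4 units/mL anti-CZP antibody at any time during the study". It plans incidence by study visit, and it plans "overall incidence by age category and by dose group". The age split is attached to the overall figure. Protocol 13.5 specifies the same overall incidence by age stratum. SAP 9 gives the age categories as 6 to 11 and 12 to 17 years. Neither document says whether age is taken at C87035 baseline or at CR0012 entry.

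**Related outputs.** Exposure (SAP 8.1) is summarized by dose group and Total, and weeks completed (SAP 7) are only listed. The autoantibody table (SAP 8.4.4) carries the note "A similar table will be presented by age group". SAP 8 says safety summaries are "presented by weight category, and by age category, as appropriate".

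**Size.** SAP 4.4 gives 16 subjects. No test between age groups is planned.

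**The concern.** An ever-positive percentage rises with the number of times a subject is tested. Here the stratifying variable, age, also sets the longest possible observation time. A child who enters at 9 can be sampled for years after one who entered at 15 has had to stop. Equal underlying risk would then tend to appear as greater immunogenicity in younger children.

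Immunogenicity is a secondary objective (Protocol 3). Because the analysis is descriptive, readers will take the raw percentages at face value. The planned tables would not warn them: follow-up is not summarized by age category, and no common window, person-time denominator or time-to-event method is specified for antibody positivity.

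**Working it through.** The documents give no sample count or incidence by age, so there is no figure of the plan's own to reproduce. The check is a model with stated assumptions.

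**Inputs from the documents**
- Stop at age 18 (Protocol 5.1.1).
- Samples at Week 14, every 12 weeks after that, and at Completion/ET and SFU (Protocol 11).
- First visits from July 2010 to June 2012 (Protocol 5.1.2); SAP approved February 2018.
- 16 subjects (SAP 4.4).

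**Assumptions, not in the documents**
- Age is uniform within each stratum. Strata are defined either by age at CR0012 entry, or by C87035 baseline age with entry 62 weeks later.
- Treatment ended by about January 2018. Calendar follow-up is then capped at 5.6 years (last entrant) to 7.5 years (first entrant).
- Dropout is exponential, at 0 to 1.0 per year.
- The per-sample risk *p* is constant and the same in both strata.

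**Formulas**
- Follow-up T = minimum of (18 − age at entry, calendar cap, dropout time), in weeks.
- Samples k = floor((T − 14)/12) + 1 + 2 for T ≥ 14. The 2 are Completion/ET and SFU; for T < 14, k = 2.
- Any-time incidence = 1 − (1 − p)^k.

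**Two single subjects, no dropout, p = 0.02, 52.18 weeks per year**
- Entry at 15: T = 3 × 52.18 = 156.5 weeks. k = floor(142.5/12) + 3 = 14. Incidence 1 − 0.98^14 = 24.6%.
- Entry at 9, cap 5.6 years: T = 292.2 weeks. k = floor(278.2/12) + 3 = 26. Incidence 1 − 0.98^26 = 40.9%.
- Entry at 9, cap 7.5 years: T = 391.4 weeks. k = floor(377.4/12) + 3 = 34. Incidence 1 − 0.98^34 = 49.7%.

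**Ratio of mean samples, younger to older stratum**

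| Dropout per year | Ratio | Scenarios covered |
|---|---|---|
| 0 | 1.8-2.7 | caps of 5.6 to 7.5 years, both age definitions |
| 0.1 | 1.7-2.4 | all caps including none, both age definitions |
| 0.25 | 1.5-1.9 | as above |
| 0.5 | 1.3-1.4 | as above |
| 1.0 | 1.1-1.2 | as above |

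**Expected any-time incidence at p = 0.02** (strata by age at entry, 6-12 vs 12-18; cap uniform on 5.6 to 7.5 years)

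| Dropout per year | Younger | Older |
|---|---|---|
| 0 | 45.0% | 24.3% |
| 0.25 | 25.1% | 17.1% |
| 0.5 | 16.9% | 13.2% |

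The incidence ratio is smaller than the sample ratio and shrinks as *p* grows. At p = 0.10 it is at most about 1.5.

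**With 16 subjects.** If true incidences were 40% and 23%, illustrative splits from 3:13 to 8:8 give a probability of about 0.67 to 0.75 that the younger stratum shows the higher observed percentage.

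**Common window to Week 50** (regular samples at Weeks 14, 26, 38 and 50; strata by C87035 baseline age; no dropout)
- Younger: 1 − 0.98^4 = 7.8%.
- Older: entry age = baseline age + 62/52.18 = baseline age + 1.19 years. Among those who enter before 18, possible follow-up is uniform on 0 to 4.81 years. Week 50 is 50/52.18 = 0.958 years, so 0.958/4.81 = 19.9% reach 18 before the fourth sample.
- Shares with k = 0, 1, 2, 3, 4 are 5.6%, 4.8%, 4.8%, 4.8% and 80.1%.
- Expected incidence = 0.048 × (0.020 + 0.040 + 0.059) + 0.801 × 0.078 = 6.8%.

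The window brings the two strata to 7.8% vs 6.8%. It reduces the imbalance but does not remove it.

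**The case against.** **The size depends on facts the documents do not give.** Neither the age distribution nor the dropout rate is stated. Protocol 6.3 requires withdrawal for repeat loss of response, certain rescue therapies, and surgery or hospitalization for Crohn's disease, so dropout could be substantial. This stands. A reader might infer that younger children get two to three times as many samples. That describes subjects who stay until 18 or the end of the study; with dropout of 0.25 to 1.0 per year the ratio is about 1.1 to 1.9.

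**The bias need not appear.** With 16 subjects, and perhaps very few under 12, the observed order can go either way. If positivity arises early or carries over from C87035, later samples add little and the gap shrinks. This also stands: the higher figure is an expectation under constant risk, not a guaranteed result.

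**The plan is partly protected.** Incidence by study visit is planned, individual concentrations are listed, and by-visit tables show the number of subjects (SAP 3.2). But the age split is attached to the overall incidence, and nothing planned shows follow-up or number tested by age.

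**Other tables.** A reader might extend the point to autoantibodies and markedly abnormal laboratory values, which follow similar 12-weekly schedules: "Autoantibody (ANA and anti-dsDNA) titers will be determined every 12 weeks starting at Week 14" (Protocol 9.6.10) and "every 12 weeks starting at Week 14, and at the Completion/Early Termination (ET) and SFU Visits" (Protocol 9.5). The documents do not support that as it stands. SAP 8.4.4 splits autoantibodies by age but states no ever-positive rule; if its unit is the sample or the visit, equal per-sample risk gives equal expected percentages. SAP 8.3 gives markedly abnormal values by dose group and Total only. An age split would come only from the general wording of SAP 8 and from Protocol 13.3, which asks for all safety summaries by age stratum.

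**Conclusion.** The point holds for anti-CZP antibody incidence in SAP 10.1. The any-time definition, 12-weekly sampling and the age-18 stop together make the age-category percentages depend on follow-up, and the SAP offers no correction. At equal constant per-sample risk the direction favors a higher expected figure in the younger stratum in every scenario tried. The size runs from modest (sample ratio 1.1-1.2 at dropout of 1.0 per year) to large (1.8-2.7 with no dropout and calendar caps). It rests on assumed uniform ages, assumed dropout and constant risk.

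The documents do not show that the observed result will be distorted in this study, nor that the laboratory or autoantibody tables share the defect. In a descriptive study of 16 subjects this is an inexpensive improvement in presentation, not a threat to the primary safety objective.

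**What to change.** In SAP 10.1:
1. Keep the crude any-time percentage by age category, as Protocol 13.5 specifies.
2. Beside it, report the first-positive rate per 100 subject-years, or a Kaplan-Meier estimate of time to first positive.
3. Add incidence in a common window to Week 50.
4. Show number tested, samples per subject and follow-up by age category. The number tested matters in the window too, since some older subjects turn 18 before all four samples.
5. State the reference date for age.

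Apply the same presentation to SAP 8.4.4 and SAP 8.3 only if those results are to be tabulated as ever-positive or ever-abnormal by age. SAP 8.4.4 should in any case say whether its unit is the subject, the visit or the sample.

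The cost is SAP wording and a few table lines from data already collected. The rates will be imprecise with 16 subjects, and the window uses fewer samples than the full period.
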